19.4. EQ-5D 5L v2

Under each heading, please tick the ONE box that best describes your health TODAY

MOBILITY

- I have no problems in walking about
- I have slight problems in walking about
- I have moderate problems in walking about
- I have severe problems in walking about
- I am unable to walk about

SELF-CARE

- I have no problems washing or dressing myself
- I have slight problems washing or dressing myself
- I have moderate problems washing or dressing myself
- I have severe problems washing or dressing myself
- I am unable to wash or dress myself

USUAL ACTIVITIES (e.g. work, study, housework, family or leisure activities)

- I have no problems doing my usual activities
- I have slight problems doing my usual activities
- I have moderate problems doing my usual activities
- I have severe problems doing my usual activities
- I am unable to do my usual activities

PAIN / DISCOMFORT

- I have no pain or discomfort
- I have slight pain or discomfort
- I have moderate pain or discomfort
- I have severe pain or discomfort
- I have extreme pain or discomfort

ANXIETY / DEPRESSION

- I am not anxious or depressed
- I am slightly anxious or depressed
- I am moderately anxious or depressed
- I am severely anxious or depressed
- I am extremely anxious or depressed

[figure not shown]
2

UK (English) v.2 © 2009 EuroQol Group. EQ-5D™ is a trade mark of the EuroQol Group

EQ-5D 5L v2

- We would like to know how good or bad your health is TODAY.
- This scale is numbered from 0 to 100.
- 100 means the best health you can imagine. 0 means the worst health you can imagine.
- Mark an X on the scale to indicate how your health is TODAY.
- Now, please write the number you marked on the scale in the box below.

YOUR HEALTH TODAY =

3
UK (English) v.2 © 2009 EuroQol Group. EQ-5D™ is a trade mark of the EuroQol Group

19.5. PROMIS Physical Function 10b Short Form

Physical Function – Short Form 10b

Please respond to each question or statement by marking one box per row.

		Without any difficulty	With a little difficulty	With some difficulty	With much difficulty	Unable to do
PFA11	Are you able to do chores such as vacuuming or yard work?	 5	 4	 3	 2	 1
PFA06	Are you able to get in and out of a car?	 5	 4	 3	 2	 1
PFA21	Are you able to go up and down stairs at a normal pace?	 5	 4	 3	 2	 1
PFA03	Are you able to run errands and shop?	 5	 4	 3	 2	 1
PFA09	Are you able to bend down and pick up clothing from the floor?	 5	 4	 3	 2	 1
PFD09-1	Are you able to lift 10 pounds (5 kg) above your shoulder?	 5	 4	 3	 2	 1
		Not at all	Very little	Somewhat	Quite a lot	Cannot do
PFA1	Does your health now limit you in doing vigorous activities, such as running, lifting heavy objects, participating in strenuous sports?	 5	 4	 3	 2	 1
PFA6	Does your health now limit you in bathing or dressing yourself?	 5	 4	 3	 2	 1
PFB3	Does your health now limit you in putting a trash bag outside?	 5	 4	 3	 2	 1
PFB44	Does your health now limit you in doing moderate activities, such as moving a table, pushing a vacuum cleaner, bowling, or playing golf?	 5	 4	 3	 2	 1

Instructions: You can use the following conversion table to translate the total raw score into a T-score for each participant. These conversions are accurate ONLY when all questions on the short form have been answered.

PROMIS-SF v2.0 Physical Function 10b Scoring Table

Adult v2.0 – Physical Function 10b		
Short Form Conversion Table		
Raw Summed Score	T-score	SE*
10	13.8	3.9
11	17.2	3.1
12	19.3	2.8
13	21.0	2.6
14	22.4	2.4
15	23.6	2.3
16	24.7	2.2
17	25.7	2.1
18	26.6	2.0
19	27.4	2.0
20	28.2	1.9
21	28.9	1.9
22	29.6	1.9
23	30.3	1.8
24	31.0	1.8
25	31.7	1.8
26	32.3	1.8
27	32.9	1.8
28	33.5	1.8
29	34.2	1.8
30	34.8	1.8
31	35.4	1.8
32	36.0	1.8
33	36.7	1.8
34	37.3	1.8
35	37.9	1.8
36	38.6	1.8
37	39.3	1.8
38	40.0	1.8
39	40.7	1.9
40	41.5	1.9
41	42.3	2.0
42	43.2	2.0
43	44.2	2.1
44	45.2	2.2
45	46.5	2.4
46	48.1	2.8
47	50.0	3.2
48	52.5	3.7
49	55.0	4.0
50	61.3	6.1

*SE = Standard Error on T-score metric

19.6. Fatigue – Short Form 13a

Please respond to each question or statement by marking one box per row.

During the past 7 days...		Not at all	A little bit	Somewhat	Quite a bit	Very much
HI7	I feel fatigued	 1	 2	 3	 4	 5
HI12	I feel weak all over	 1	 2	 3	 4	 5
AN1	I feel listless ("washed out").....	 1	 2	 3	 4	 5
AN2	I feel tired	 1	 2	 3	 4	 5
AN3	I have trouble starting things because I am tired.....	 1	 2	 3	 4	 5
AN4	I have trouble finishing things because I am tired.....	 1	 2	 3	 4	 5
AN5	I have energy	 5	 4	 3	 2	 1
AN7	I am able to do my usual activities	 5	 4	 3	 2	 1
AN8	I need to sleep during the day.....	 1	 2	 3	 4	 5
AN12	I am too tired to eat	 1	 2	 3	 4	 5
AN14	I need help doing my usual activities	 1	 2	 3	 4	 5
AN15	I am frustrated by being too tired to do the things I want to do.....	 1	 2	 3	 4	 5
AN16	I have to limit my social activity because I am tired.....	 1	 2	 3	 4	 5

Instructions: You can use the following conversion table to translate the total raw score into a T-score for each participant. These conversions are accurate ONLY when all questions on the short form have been answered.

PROMIS-SF v1.0 Fatigue 13a Scoring Table

Fatigue 13a (FACIT-Fatigue) - Adult v1.0					
Short Form Conversion Table					
Raw Score	T-score	SE*	Raw Score	T-score	SE*
13	30.3	4.7	40	60.8	1.8
14	35.0	3.5	41	61.4	1.8
15	38.0	3.0	42	62.0	1.8
16	40.3	2.8	43	62.6	1.8
17	42.1	2.6	44	63.2	1.8
18	43.7	2.5	45	63.8	1.8
19	45.0	2.3	46	64.4	1.8
20	46.3	2.2	47	65.0	1.8
21	47.3	2.1	48	65.6	1.8
22	48.3	2.0	49	66.2	1.9
23	49.3	2.0	50	66.9	1.9
24	50.1	1.9	51	67.5	1.9
25	51.0	1.9	52	68.2	1.9
26	51.7	1.9	53	68.9	2.0
27	52.5	1.9	54	69.6	2.0
28	53.2	1.9	55	70.4	2.0
29	53.9	1.8	56	71.2	2.1
30	54.6	1.8	57	72.0	2.2
31	55.3	1.8	58	72.9	2.3
32	55.9	1.8	59	73.9	2.4
33	56.6	1.8	60	75.0	2.5
34	57.2	1.8	61	76.2	2.7
35	57.8	1.8	62	77.5	2.9
36	58.4	1.8	63	79.1	3.1
37	59.0	1.8	64	81.2	3.3
38	59.6	1.8	65	83.5	3.4
39	60.2	1.8			

*SE = Standard Error on T-score metric

19.7. An Adjusted Difference in Proportions using Logistic Regression

The method was proposed by Ge et al. (2011). Please ensure the model built in this macro is the same with logistic regression model which is used for odds ratio calculation.

%macro LR (

data=, /* input data set */

var1=, /* continuous covariates in the logistic regression */

var2=, /* categorical covariates in the logistic regression */

p1=, /* number of continuous covariates in the logistic regression */

p2=, /* number of categorical covariates in the logistic regression */

resp=, /* binary response variable in the logistic regression */

ntrt=); /* position of the treatment variable in the categorical covariates */

/* delete the observations with missing values in either numeric or categorical covariates */

```
data newdata;
set &data;
if cmiss(of &var1 &var2)>0 then delete;
run;
/* extract the design matrix and variance-covariance matrix of the regression and store them in
data1 and parms respectively */
/* cases when there is no continuous covariates */
%if &p1=0 %then
%do;
proc transreg data=newdata dummy noprint;
model identity(&resp) = class(&var2/zero=first);
output out = data1(drop=_: &var2 &resp) replace;
run;
proc logistic data=newdata desc covout outest=parms(drop=_:)
noprint;
class &var2 / param=ref ref=first;
model &resp = &var2;
run;
%end;
/* cases when both categorical and continuous covariates exist */
%else
%do;
proc transreg data=newdata dummy noprint;
model identity(&resp) = class(&var2/zero=first) identity(&var1);
output out = data1(drop=_: &var2 &resp) replace;
run;
proc logistic data=newdata desc covout outest=parms(drop=_:)
noprint;
class &var2 / param=ref ref=first;
model &resp = &var2 &var1;
run;
%end;
/* estimate the proportion difference and standard error to construct the 95% confidence
interval */
```

```
proc iml;
use parms;
read all into parms;
close parms;
use data1;
read all into xmat;
close data1;
p = nrow(params)-2;
cov = params[2:(p+2),];
psize = nrow(xmat);
ntrt = &ntrt+1;
xt = xmat;
xt[,ntrt] = J(psize,1,1);
axT = xt*params[1,];
xc = xmat;
xc[,ntrt] = J(psize,1,0);
axC = xc*params[1,];
pderT = J(psize,1,0);
pderC = J(psize,1,0);
pderivT = J(psize,(p+1),0);
pderivC = J(psize,(p+1),0);
gt = J(1,(p+1),0);
gc = J(1,(p+1),0);
do k=1 to psize;
pderT[k] = exp(axT[k])/(1+exp(axT[k]));
pderC[k] = exp(axC[k])/(1+exp(axC[k]));
pderivT[k,] = pderT[k]*(1-pderT[k])*xt[k,];
pderivC[k,] = pderC[k]*(1-pderC[k])*xc[k,];
end;
difb=sum(pderT-pderC)/psize;
pT=sum(pderT)/psize;
pC=sum(pderC)/psize;
do k=1 to (p+1);
gt[k] = sum(pderivT[,k])/psize;
```

```

gc[k] = sum(pderivC[,k])/psize;
end;
se=sqrt(gt*cov*gt`+ gc*cov*gc`-2*gt*cov*gc`);
upperb=difb+1.96*se;
lowerb=difb-1.96*se;
store difb se pT pC lowerb upperb;
create difb var {"difb" "se" "pT" "pC" "lowerb" "upperb"}; **output statistics;
append;
close difb;
quit;
%mend;
/* print out the LR estimation results */

```

19.8. PRO Appendix for PROMIS

19.8.1. Distribution-based Minimal Clinically Important Difference (MCID)

The distribution-based minimal clinically important difference (MCID), $\frac{1}{2}$ SD and 1 SEM will be provided based on the pooled PROMIS Physical Function scores and Fatigue scores of two treatment arms at baseline for the FAS and the PPS, respectively.

$\frac{1}{2}$ SD = $1/2$ * Standard Deviation of the pooled norm-based T-scores of two treatment arms at baseline

1 SEM = $[(1 - \text{Cronbach's alpha})^{(1/2)}] * \text{SD}$

Where SD is the same as the definition for $\frac{1}{2}$ SD and Cronbach's alpha refers to the Standardized Cronbach's alpha calculated using the following SAS code. For example, when calculating Cronbach's alpha for PROMIS Physical Function, the individuals' 10 item scores that constituted the Physical Function score will be used in the VAR clause.

Sample SAS code:

```

ODS OUTPUT CronbachAlpha=CronbachAlpha;
PROC CORR DATA = PF NOMISS ALPHA;
VAR pfa11 pfa56 pfa21 pfa53 pfa9 pfb28r1 pfa1 pfa6 pfb3 pfb44;
RUN;

```

19.8.2. Sensitivity Analysis of PROMIS

Sensitivity analysis will be conducted using Analysis of Covariance (ANCOVA) model for PROMIS Physical Function T-scores and Fatigue T-scores using Last Observation Carries Forward (LOCF) imputation for the FAS and the PPS, respectively. The LOCF imputation should be performed after any data handling for the intercurrent events as described in [Section 12.3.3.6](#) and [Section 12.3.3.7](#).

An ANCOVA model with treatment and stratification factors as fixed effects, the baseline score value as covariate will be used to assess treatment difference. The LSM and the corresponding 95% confidence intervals for the differences between roxadustat and the placebo group (roxadustat – placebo) will be presented along with the p-values for the treatment differences resulting from the model. The LSM for the difference will be considered clinically meaningful if it exceeds the MCID and will be marked in the results, see [Section 19.8.1](#) for details of MCID.

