**Appendix B - Patients who Discontinue Study Medication Prior to Week 52**

Procedures	EOT 	Post - EOT 	Every 8 weeks assessment from Post-EOT WK 4 visit. Last visit at Week 52 from first dose.	
		WK 4	WK 12	→
Informed consent signature				
Eligibility Review 				
Med History/ Demographics				
Physical Exam	X	X		
Weight 				
HbsAg, anti-HCV AB, HIV				
Endogenous serum EPO Level 	X	X	X	
B12, Folate	X	X		
PK 				
ECG 	X	X		
Bone marrow aspirate and biopsy 	X			
Vital signs 	X	X	X	
ECOG Score 	X	X		
Serum Lipid Panel	X	X		
LFTs 	X	X	X	
Serum chemistry 	X	X	X	
PT, PTT	X	X		
Hepcidin	X	X	X	
Pregnancy test 	X	X		
C-reactive protein	X	X		
Recording of transfusions 	→			
CBC 	X	X	X	
Local Hemoglobin	X	X	X	
Reticulocyte count; CHr	X	X		
Iron Biomarkers 	X	X	X	
Registration/Randomization to the study				
HRQoL Questionnaires 	X	X		
Study drug dosing				
Study drug dispensation				
Dose adjustment review				
AEs/Con Meds/Procedures	→			

For footnotes please refer to [Appendix A](#)

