12.3.2. Sequential Gatekeeping Procedure

Once the primary hypothesis has been rejected for the primary endpoint, the primary endpoint at week 52 and the secondary endpoints in the order specified in the Table 4 will be tested using a sequential gatekeeping procedure, in order to maintain the overall two-sided type I error of 0.05. If p-value from a test is < 0.05 , the claim of superiority will be considered successful, and the test will progress to the next comparison in sequence as follows.

Table 4: Sequential Gatekeeping Procedure

Test	Variable	Comparison
1	Proportion of patients who achieved TI ≥ 56 consecutive days (e.g., 8 weeks) since first dose in the first 28-weeks of treatment	Superiority of roxadustat versus placebo
2	Proportion of patients who achieved TI ≥ 56 consecutive days (e.g., 8 weeks) since first dose in the 52-weeks of treatment	Superiority of roxadustat versus placebo
3	Proportion of patients who achieved TI ≥ 56 consecutive days (e.g., 8 weeks) anytime during the study	Superiority of roxadustat versus placebo
4	Proportion of patients who achieved $\geq 50\%$ reduction in number of pRBC transfusions over 8 weeks compared to their Baseline for any 8-week period during the study	Superiority of roxadustat versus placebo
5	Cumulative number of patient-exposure-weeks (PEW) of TI over the first 28 weeks of the treatment period	Superiority of roxadustat versus placebo
6	Number of pRBC transfused change from baseline over the first 28 weeks of the treatment period	Superiority of roxadustat versus placebo
7	Proportion of patients who achieved TI for ≥ 20 consecutive weeks (140 consecutive Days)	Superiority of roxadustat versus placebo

8	Mean change from baseline in the PROMIS-SF v2.0 Physical Function 10b score at week 9	Superiority of roxadustat versus placebo
9	Mean change from baseline in the PROMIS-SF v1.0 Fatigue 13a score at week 9	Superiority of roxadustat versus placebo
10	Mean change from baseline in EQ-5D-5L VAS score at week 9	Superiority of roxadustat versus placebo

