12.3.3.6. Mean Change from Baseline in Physical Functioning Subscale of PROMIS

The PROMIS PF item measures self-reported, current capability to carry out activities that require physical actions, ranging from self-care (activities of daily living) to more complex activities that require a combination of skills, often within a social context. The questionnaire will be administered at the Week 1 Day 1, Week 9, Week 17, Week 28 and Week 52 (or EOT). The PF 10-item short form which contains 10 questions will be used in this study, and each item is scored on a 5-point rating scale, with higher scores indicating better functioning. To find the total raw score, sum the values of the response to each question, with the lowest possible raw score is 10; the highest possible raw score is 50.

PROMIS items are not scored as sums, but rather on a standardized T-score metric ([Appendix 19.5](#)) using IRT. The standardized norm-based T-scores will be used in the summary. The mean change from Baseline in the PROMIS-SF v2.0 Physical Function 10b score will be summarized and analyzed. A mixed model for repeated measures (MMRM) with treatment, visit, treatment*visit, and stratification factors as fixed effects, the baseline score value and baseline*visit interaction as covariate will be used to assess treatment difference. The LSM and the corresponding 95% confidence intervals for the differences between roxadustat and the placebo group (roxadustat – placebo) will be presented along with the p-values for the treatment differences resulting from the model. The LSM for the difference will be considered clinically meaningful if it exceeds the distribution-based minimal clinically important difference (MCID) and will be marked in the results, see [Section 19.8.1](#) for details of MCID. An unstructured variance-covariance structure will be used to model the within-patient errors. This variance-covariance matrix will be estimated across treatment groups. If the model fails to converge, then the covariance structure that converges and with the highest REML log likelihood will be used.

Missing values will be handled by the MMRM model, utilizing data from all visits and all patients.

A sensitivity analysis will be conducted using Analysis of Covariance (ANCOVA) model with Last Observation Carries Forward (LOCF) imputation, see [Section 19.8.3](#) for details.

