12.3.3.7. Mean Change from Baseline in Fatigue Subscale of PROMIS

Fatigue will be measured in the study using the 13-item fatigue scale of the FACIT Measurement System, each item is scored on a 5-point rating scale ranging from 1 to 5 depicting “not at all” to “very much”, with higher scores indicating better functioning. The questionnaire is designed for self-completion by patients and will be administered at baseline, Week 9, Week 17, Week 28 and Week 52(or EOT).

PROMIS items are not scored as sums, but rather on a standardized T-score metric ([Appendix 19.6](#)) using IRT. The standardized norm-based T-scores will be used in the summary. The mean change from Baseline in the PROMIS-SF v1.0 Fatigue 13a score over time will be summarized and analyzed using the FAS and PPS Population. The analysis window is defined in [Appendix 19.3.1](#).

A mixed model for repeated measures (MMRM) with treatment, visit, treatment*visit, and stratification factors as fixed effects, the baseline score value and baseline*visit interaction as covariate will be used to assess treatment difference. The LSM and the corresponding 95% confidence intervals for the differences between roxadustat and the placebo group (roxadustat – placebo) will be presented along with the p-values for the treatment differences resulting from the model. The LSM for the difference will be considered clinically meaningful if it exceeds the distribution-based minimal clinically important difference (MCID) and will be marked in the results, see [Section 19.8.1](#) for details of MCID. An unstructured variance-covariance structure will be used to model the within-patient errors. This variance-covariance matrix will be estimated across treatment groups. If the model fails to converge, then the covariance structure that converges and with the highest REML log likelihood will be used.

Missing value will be handled by the MMRM model, utilizing data from all visits and all patients.

A sensitivity analysis will be conducted using Analysis of Covariance (ANCOVA) model with Last Observation Carries Forward (LOCF) imputation, see [Section 19.8.2](#) for details.

Week 9 and week 52 are the analysis endpoint for 28-week and 52-week analysis respectively, the p-value obtained will be reported.

This analysis will take into account the potential intercurrent events as follows:

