17. CHANGES FROM THE PROTOCOL-SPECIFIED ANALYSES

3. Exploratory analyses on time to transfusion independence and time to 50% reduction in pRBC transfusion are added in this SAP due to clinical interest, although they are not in the protocol.
4. The 52 weeks analysis on the primary endpoint is regarded as a secondary endpoint and been included in the sequential gatekeeping procedure.
5. Based on results from prior roxadustat studies, measuring HRQoL 2-4 weeks after Hb “peaks” or stabilizes is shown to be most informative. In order to capture the treatment effect on Physical Function/fatigue before it wears off, Week 9 will be used as the primary time-point for HRQoL hypothesis testing in the sequential gatekeeping procedure.
6. Based on the re-estimated sample size of 120, 140 patients were enrolled in the double-blind component of the study.

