^a: Relative to the first study medication date. For example, Day 1 = the first dose date of study medication.

^b: Week 28 visit should be conducted at the end of 28 weeks of treatment (2 weeks after Week 27 Visit).

^c: Week 52 Visit should be scheduled at the end of 52 weeks treatment (6 weeks after Week 47 visit).

**Table 7.6 Analysis Visit Windows for CBC
(Only in Subjects Enrolled before Effective Day of Protocol Amendment 3)**

Analysis Visit	Visit Scheduled Day ^a	Window
Baseline	Day 1	Up to Day 1 Pre-Dose
Week 2	Day 7*(Week # -1)+1	[Day 1 Post-Dose, Scheduled Day +3]
Week 3,4	Day 7*(Week # -1)+1	[Scheduled Day -3, Scheduled Day +3]
Week 5	Day 7*(Week # -1)+1	[Scheduled Day -3, Scheduled Day +7]
Weeks 7, 9, 11...27	Day 7*(Week # -1)+1	[Scheduled Day -7, Scheduled Day +7]
Week 28 ^b	Day 7*(Week #)+1	[Scheduled Day -7, Scheduled Day +7]
Weeks 31	Day 7*(Week # -1)+1	[Scheduled Day -7, Scheduled Day +14]
Week 35, 39, 43	Day 7*(Week # -1)+1	[Scheduled Day -14, Scheduled Day +14]
Week 47	Day 7*(Week # -1)+1	[Scheduled Day -14, Scheduled Day +21]
Week 52 ^c	Day 7*(Week #)+1	[Scheduled Day -21, Up to Week 4 Follow up)

^a: Relative to the first study medication date. For example, Day 1 = the first dose date of study medication.

^b: Week 28 visit should be conducted at the end of 28 weeks of treatment (2 weeks after Week 27 Visit).

^c: Week 52 Visit should be scheduled at the end of 52 weeks treatment (6 weeks after Week 47 visit).

Table 7.7 Analysis Visit Windows for EQ-5D-5L, PROMIS Physical Function and PROMIS Fatigue Function

Derived Visit	Visit Scheduled Day ^a	Window
Baseline	Day 1(first dose day)	Up to Day 1 Pre-Dose
Week 9	Day 7 * (Week # -1) +1	[Day 1 post-dose, Scheduled Day + 28)
Weeks 17	Day 7 * (Week # -1) +1	[Scheduled Day - 28, Scheduled Day + 42)
Week 28 ^b	Day 7 * (Week #) +1	[Scheduled Day - 42, Scheduled Day + 84)
Week 52 ^c	Day 7 * (Week #) +1	[Scheduled Day - 84, Up to Week 4 follow-up)

^a: Relative to the first study medication date. For example, Day 1 = the first dose date of study medication.

^b: Week 28 visit should be conducted at the end of 28 weeks of treatment (2 weeks after Week 27 Visit).

^c: Week 52 Visit should be scheduled at the end of 52 weeks treatment (6 weeks after Week 47 visit).

Table 7.8 Analysis Visit Windows for ECOG

Derived Visit	Visit Scheduled Day ^a	Window
Baseline	Day 1(first dose day)	Up to Day 1 Pre-Dose
Week 5	Day 7 * (Week # -1) +1	[Day 1 post-dose, Scheduled Day + 28)

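### At Week 9, LOCF for the two gatekept PROMIS tests reduces to baseline carried forward or available cases, so it does not adequately stress the missing-at-random assumption

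*SAP*

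**What the plan says.** **Endpoints.** SAP Section 12.3.2, Table 4, lists Test 8 as "Mean change from baseline in the PROMIS-SF v2.0 Physical Function 10b score at week 9" and Test 9 as "Mean change from baseline in the PROMIS-SF v1.0 Fatigue 13a score at week 9". Section 17, item 5, gives the choice of time point: "Week 9 will be used as the primary time-point for HRQoL hypothesis testing in the sequential gatekeeping procedure".

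**Schedule.** Section 12.3.3.6 says for Physical Function: "The questionnaire will be administered at the Week 1 Day 1, Week 9, Week 17, Week 28 and Week 52 (or EOT". Section 12.3.3.7 has Fatigue "administered at baseline, Week 9, Week 17, Week 28 and Week 52(or EOT".

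**Window.** In Section 19.3.1, Table 7.7, the Week 9 window for the questionnaires is "Day 1 post-dose, Scheduled Day + 28", with the upper end excluded. If several forms fall in a window, the last is used.

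**Early stoppers.** Protocol Appendix B marks "HRQoL Questionnaires" at the EOT visit and four weeks later, but not at the subsequent eight-weekly visits.

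**Missing scores.** The main analysis is an MMRM on all visits. After discontinuation for an AE or SAE, missing scores are first set to the worst possible value (Sections 12.3.3.6 and 12.3.3.7). To fill what is left, Section 19.8.2 plans an ANCOVA on Physical Function and "Fatigue T-scores using Last Observation Carries Forward (LOCF) imputation for the FAS and the PPS, respectively". It names no time point and does not say whether a baseline score may be carried. Section 12.3.3.6 refers to a Section 19.8.3 for this analysis, but the contents list stops at 19.8.2.

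**The concern.** A sensitivity analysis for missing data should ask how far the unseen outcomes must depart from the main model's assumption before the conclusion changes. The MMRM assumes that, given the observed scores and covariates, patients with a missing Week 9 score resemble those with an observed one. The worrying departure is that they did worse. If LOCF has nothing but Day 1 to carry, it cannot represent that departure. Agreement between LOCF and the MMRM on Tests 8 and 9 would then say little about robustness, although both tests carry alpha in the fixed sequence.

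**Working it through.** The plan gives no power, SD, effect or missing rate for Tests 8 and 9, so there is no stated figure to reproduce.

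**Step 1: can any post-baseline score precede the Week 9 value?** From Table 7.7:
- Week 9 scheduled day = 7 × (9 − 1) + 1 = 57. The window runs from Day 1 post-dose to before Day 57 + 28 = 85.
- Week 17 scheduled day = 7 × (17 − 1) + 1 = 113. The window runs from Day 113 − 28 = 85 to before Day 113 + 42 = 155.

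The windows meet at Day 85 and the first opens after the first dose. An EOT form completed before Day 85 is itself a Week 9 value. So when Week 9 is missing, only Day 1 is available to carry.

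**Step 2: who is still missing at that point?** AE/SAE discontinuers have already been given the worst score. The rest are patients who stopped for other reasons without an EOT form, missed forms, and deaths before any post-baseline form. In the PPS there is less to fill, because Section 5.3.3 requires at least 8 weeks of treatment.

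**Step 3: what each reading estimates.** Let cR and cP be the mean changes among observed patients, and mR and mP the missing shares.
- Missing patients resemble observed ones: cR − cP.
- Only post-baseline scores carried: nothing is imputed, giving an available-case ANCOVA that also estimates cR − cP.
- Baseline carried: (1 − mR)cR − (1 − mP)cP. With cR = 3 and cP = 0, this is 0.9 × 3 = 2.7 at 10% missing in both arms and 0.8 × 3 = 2.4 at 20%.

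**Step 4: missing patients worse than baseline.** Assume cR = 4, cP = 0, equal missing shares m, and missing roxadustat patients 8 points below observed ones, so 4 points below baseline. The full-data effect is 4 − 8m, baseline carried gives 4(1 − m), and available-case gives 4.

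| Missing share | Full data | Baseline carried | Available-case |
|---|---|---|---|
| 5% | 3.6 | 3.8 | 4.0 |
| 10% | 3.2 | 3.6 | 4.0 |
| 20% | 2.4 | 3.2 | 4.0 |
| 30% | 1.6 | 2.8 | 4.0 |

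Simulated ANCOVAs with 84 and 56 patients agree. The split assumes 3:2 on the 140 enrolled (SAP Section 17); SD 8 and baseline correlation 0.6 are also assumed. At 20% missing the estimates were 2.40, 3.22 and 4.03, with significance in 53%, 87% and 89% of runs. The simulations did not include the MMRM itself.

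With cP = 0, baseline carried is optimistic exactly when missing roxadustat patients are on average below their baseline, and that is the case it cannot represent.

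**The case against.** A reader might infer that the check is empty and could never disagree with the MMRM. The documents do not support that. Section 19.8.2 leaves open carrying baseline. On that reading the analysis makes a different assumption from the MMRM, brings in patients with only a Day 1 score, and moves the estimate. It can also reverse a result. In simulations with the same settings, an effect of 3 and data missing at random, it removed significance from about 4% of significant available-case results at 10% missing in both arms, 7% at 20% in both, and 14% at 20% on roxadustat against 5% on placebo. The check is empty as an imputation only if carrying is limited to post-baseline scores.

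A reader might also infer that patients who stop because of side effects are credited with no change. They are not: the worst-score rule comes first. EOT forms can supply further Week 9 values.

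A contrast with worst-score imputation is tempting too. Eight roxadustat patients of 84 at an assumed baseline T of 40 would move the arm mean by 8 × (40 − 13.8)/84 = 2.5 points, against 0.10 × 3 = 0.3 for baseline carried. But the plan already uses the worst score where it judges it apt, and nothing shows it plausible for the remaining patients. Nor does carrying baseline always shrink the treatment difference: with cR = 3, cP = 1, mR = 5% and mP = 20%, it gives 2.85 − 0.80 = 2.05 against 2.

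Two limits on importance stand. Tests 8 and 9 are reached only if Tests 1 to 7 all succeed, and the MMRM remains the confirmatory analysis. LOCF also has Week 9, 17 and 28 scores to carry at Week 52, so the point does not extend there. What survives is that at Week 9 the single alternative assumption is unspecified and stops at zero change.

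**Conclusion.** The point holds for Week 9. LOCF there is either baseline carried forward or an available-case ANCOVA, the SAP does not say which, and neither represents missing patients who did worse than baseline. This follows from the schedule and Table 7.7 alone.

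The size does not. The documents give no Week 9 missing rate, SD or effect, and the residual group may be small once the worst-score rule and EOT forms have been applied. Under the assumptions shown, the overstatement from carrying baseline runs from 0.2 T points at 5% missing to 1.2 at 30% (4(1 − m) − (4 − 8m) = 4m), and from available cases from 0.4 to 2.4 (8m). If missing patients stay at or above baseline, baseline carried is not optimistic in this set-up.

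The plan should be changed, because what can be said about the robustness of Tests 8 and 9 depends on it. The primary endpoint is untouched. The documents do not show when LOCF was chosen relative to the move to Week 9, so no inference about that is drawn.

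**What to change.** 1. In Section 19.8.2, confine LOCF, if it is wanted, to Week 52.
2. For Week 9, after the worst-score substitution for AE/SAE discontinuers, multiply impute the scores still missing, with roxadustat values drawn from the placebo distribution (reference-based).
3. Follow with a delta tipping-point analysis: worsen the imputed roxadustat scores stepwise until p ≥ 0.05, and report the delta at which this happens.
4. State the worsening direction for each scale. It is downward for Physical Function and VAS. For Fatigue, the form and conversion table in Section 19.6 score more fatigue higher, whereas Section 12.3.3.7 says higher is better. Reconcile these, and give the worst possible score as a number.
5. State how deaths before Week 9 are handled.
6. Apply the same to EQ-5D VAS (Test 10), for which Section 12.3.3.8 plans no sensitivity analysis of the missing-data assumption.
7. Correct the reference to Section 19.8.3.

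The cost is SAP wording and modest programming, with no new data. The supportive result may look less favourable than LOCF would. It should be specified before unblinding; added later, it would be post hoc.
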